# 7.2 GEN1044 Dose Modification Guidance and Safety Stopping Criteria

#### 7.2.1 Dose Escalation Part

- In the event a subject experiences an AE that meets DLT criteria as outlined in Section 7.1, treatment must be permanently discontinued (unless the subject per investigator's discretion has recovered or is expected to recover and expected to benefit from continued treatment). GEN1044 should also be held for the following:
  - If platelet count  $<50\times10^9$ /L, hold dose until platelet count is  $\ge50\times10^9$ /L.
  - If febrile neutropenia  $<0.5\times10^9$ /L, hold dose until neutrophil count is  $\ge0.5\times10^9$ /L.
  - o If hemoglobin is  $\leq 8 \text{ g/dL}$  ( $\leq 5 \text{ mmol/L}$ ), hold dose until hemoglobin  $\geq 8 \text{ g/mL}$  ( $\geq 5 \text{ mmol/L}$ ).
  - **Note**: Transfusion with blood products and/or administration with G-CSF is permitted if needed (see Section 6.5.2.2).
- During the trial, a planned dose of GEN1044 can be postponed for up to 6 weeks for an AE, whether it is considered drug-related or not; a delay of >6 weeks requires permanent discontinuation of treatment. The delay might be extended to 12 weeks after consultation with the sponsor medical monitor.
- First episodes of cytokine blockade-refractory grade 3 CRS or ICANS (see Section 10.4.1) lasting >72 hours require permanent discontinuation from trial treatment.
- First episodes of refractory grade 4 CRS or ICANS require permanent discontinuation from trial treatment.
- Refer to Appendix 7, Table 27, for dose modification guidelines for specific adverse events. For dose escalation, these rules will only apply after the DLT period.

Version: 4.0

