For subjects in the Dose Escalation part who receive GEN1044 doses beyond the DLT evaluation period, all AEs corresponding to the definition of DLT (see Section 7.1) will be considered for the purpose of determining the RP2D. For the selection of the recommended dose for treatment of the Expansion cohorts and for further development, all drug-related AEs will be taken into consideration.

The concept of the design of the trial is shown in Section 1.2, Figure 1 . The Dose Escalation part will consist of dose-level (DL) cohorts. The Expansion part will consist of parallel cohorts, by type of cancer.

[figure not shown]

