#### 7 DOSE MODIFICATIONS AND SAFETY MANAGEMENT GUIDELINES

# 7.1 **Dose-Limiting Toxicity**

The DLT evaluation period is defined as the period from the start of the first GEN1044 administration on C1D1 of the Dose Escalation part of the trial until 7 days after the first full dose. As described in Section 4.1, if a subject receives the priming dose on C1D1, one intermediate dose on C1D8, and the full dose starting on C1D15, the DLT period will be the first 21 days of Cycle 1 (Cycle 1 days 1 through 21). If a subject receives the priming dose on C1D1, the first intermediate dose on C1D8, the second intermediate dose on C1D15, and the first full dose on C2D1, the DLT period will be Cycle 1 up to and including C2D7 (ie, a total of 28 days). The DLT evaluation period may be adjusted for potential GEN1044 treatment delay as described in Section 11.1.7.

National Cancer Institute (NCI) Common Terminology Criteria for Adverse Events (CTCAE) v5.0 (NCI-CTCAE, 2017) will be used to assess toxicities/AEs, except for CRS and immune effector cell-associated neurotoxicity syndrome (ICANS) (see Section 10.4.1 and Section 10.4.2, respectively).

A DEC is set up for the study. The DEC will review data from each DL cohort and make a decision regarding dose escalation. That decision of the DEC has to be confirmed by the sponsor SC. The DMC will review data on a quarterly basis.

Events to be collected and assessed by the DMC for DLTs include: SAEs; AESIs where applicable; and clinically significant abnormal laboratory values (that are not already covered by a separate AE term).

The occurrence of any of the toxicities outlined in this section will be considered a DLT if assessed by the investigator to be at least possibly related to GEN1044. AEs clearly not related to the trial treatment (GEN1044) such as disease progression, environmental factors, unrelated trauma, etc, should not be considered a toxicity event.

The following will qualify for a DLT:

- ≥ Grade 3 CRS, graded according to American Society for Transplantation and Cellular Therapy (ASTCT) criteria (Lee et al., 2019) (see Section 10.4.1, Table 16).
- \geq Grade 3 ICANS, graded according to the criteria specified in Table 17, Section 10.4.2.
- Any Grade 3 or 4 non-hematologic toxicity except for:
  - Grade ≥ 3 nausea/vomiting or diarrhea <72 hours with adequate anti-emetic and other supportive care
  - Grade  $\geq$  3 fatigue  $\leq$ 1 week

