  - Grade ≥ 3 electrolyte abnormality that lasts <72 hours, unless the patient has clinical symptoms, in which case all grade ≥3 electrolyte abnormality regardless of duration should count as a DLT
  - Grade ≥ 3 amylase or lipase elevation NOT associated with symptoms or clinical manifestations of pancreatitis does not need to be counted as a DLT
  - o Laboratory abnormalities are excluded except for below:
    - Clinically significant medical intervention is required to treat the subject, OR
    - The abnormality leads to hospitalization, OR
    - The abnormality persists for >1 week, OR
    - The abnormality results in a drug-induced liver injury (DILI)
- Any Grade 3 or 4 hematologic toxicity, except for:

Version: 4.0

- Grade  $\geq$  3 lymphocytopenia lasting  $\leq$ 72 hours
- Grade 3 thrombocytopenia not associated with impaired hemostasis, clinically significant bleeding or required platelet transfusion therapy
- Grade  $\geq$  3 ANC lasting <7 days and without fever
- Grade 3 or grade 4 febrile neutropenia:
  - o Grade 3 is defined as absolute neutrophil count (ANC) <1000/mm³ with a single temperature of >38.3°C (101°F) or a sustained temperature of ≥38°C (100.4°F) for more than 1 hour.
  - o Grade 4 is defined as ANC <500/mm³ with a single temperature of >38.3°C (101°F) or a sustained temperature of ≥38°C (100.4°F) for more than 1 hour, with life-threatening consequences and urgent intervention indicated.
- Liver toxicity as defined by Hy's Law (FDA-Guidance, 2009) below:
  - o Aminotransferase (ALT and/or AST) >3×ULN.
  - o Total bilirubin >2×ULN, without initial findings of cholestasis (elevated serum alkaline phosphatase).
  - No other reason can be found to explain the combination of increased ALT/AST and total bilirubin.
- Any treatment-related toxicity that causes the subject to discontinue treatment during Cycle 1.
- Any grade 5 toxicity.

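### After the DLT period in escalation, Section 7.2.1 allows an investigator override for non-refractory grade 4 CRS or ICANS, Table 27 requires a permanent stop, and nothing says which prevails

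*Protocol*

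**What the plan says.** **Section 7.2.1 (escalation).** The first bullet says that treatment must stop permanently after an adverse event meeting the Section 7.1 criteria, "unless the subject per investigator's discretion has recovered or is expected to recover and expected to benefit from continued treatment". A later bullet removes the exception for one class of grade 4 event: "First episodes of refractory grade 4 CRS or ICANS require permanent discontinuation from trial treatment". The last bullet refers to Appendix 7, Table 27, and adds: "For dose escalation, these rules will only apply after the DLT period".

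**Section 7.1.** The CRS criterion, preceded by a greater-than-or-equal sign, is "Grade 3 CRS, graded according to American Society for Transplantation and Cellular Therapy (ASTCT) criteria". ICANS has the same threshold. Every grade 4 CRS or ICANS event therefore meets the criteria that trigger the first bullet of 7.2.1.

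**Appendix 7, Table 27.** The grade 4 CRS or ICANS row requires permanent discontinuation, with no refractory condition and no investigator exception. The table note repeats that in escalation the rules apply after the DLT period. The hepatic block requires the same action for a first grade 4 event.

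**Section 7.2.2 (expansion).** Any grade 4 CRS or ICANS ends treatment, in line with Table 27.

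**Sections 7.3 and 10.1.4.** A grade 4 infusion-related reaction ends treatment in both parts. Such reactions are events that begin during the infusion or within 24 hours after it, subject to the investigator's assessment.

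**The concern.** Take an escalation subject, past the DLT period, with a first grade 4 CRS that responds to tocilizumab and resolves. Under the 7.2.1 bullets the investigator may resume GEN1044 on judging that the subject has recovered and should benefit. Under Table 27, which is in force at that point, treatment is over. What is at stake is re-dosing after a life-threatening event. By Table 16, grade 4 CRS means at least two vasopressors or positive pressure ventilation. By Table 17, grade 4 ICANS includes coma, prolonged life-threatening seizure and diffuse cerebral edema.

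The qualifier is also unclear. The grade 3 bullet of 7.2.1 specifies cytokine blockade and more than 72 hours; the grade 4 bullet says only refractory. Table 27's footnote on adequate tocilizumab treatment (three doses within 24 hours) is attached to the grade 3 row, not the grade 4 row.

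**Working it through.** The plan gives no figure on this point, so the check compares the texts case by case.

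| Situation | Section 7.2.1 bullets | Table 27 | Result |
|---|---|---|---|
| Escalation, inside DLT period, grade 4 CRS/ICANS | Stop if refractory; otherwise stop by default, with override | Not in force | No conflict |
| Escalation, after DLT period, refractory first grade 4 CRS/ICANS | Stop | Stop | Agree |
| Escalation, after DLT period, non-refractory grade 4, judged an infusion-related reaction | Stop by default, with override | Stop | Conflict, but Section 7.3 already forces the stop |
| Escalation, after DLT period, non-refractory grade 4, not judged an infusion-related reaction | Stop by default, with override | Stop | Conflict, nothing settles it |
| Escalation, after DLT period, first grade 4 hepatic event meeting DLT criteria | Stop by default, with override | Stop | Conflict |
| Escalation, after DLT period, first grade 4 hepatic event not meeting DLT criteria | DLT bullet not triggered | Stop | No conflict |
| Expansion, any grade 4 CRS/ICANS | Not applicable; 7.2.2 says stop | Stop | Agree |

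**The hepatic rows.** Section 7.1 counts "Any Grade 3 or 4 non-hematologic toxicity except for" a list of exceptions, among them "Laboratory abnormalities are excluded except for below". A laboratory abnormality then counts if it needs clinically significant intervention, leads to hospitalization, lasts more than 1 week or results in drug-induced liver injury. Liver toxicity meeting Hy's Law is a separate criterion. Only events that qualify in one of these ways fall under the override.

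**Do the 7.2.1 bullets reach beyond the DLT period?** The CRS/ICANS bullets carry no time limit. In 7.2.1 only the Table 27 bullet is expressly confined to one side of the DLT period. The delay bullet is expressly wider: "During the trial, a planned dose of GEN1044 can be postponed for up to 6 weeks for an AE". That shows the section is not confined to the DLT period as a whole; it does not by itself fix the reach of the other bullets.

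**Size of the affected period (version 4.0 regimens, no delays).**
- Weekly doses in Cycles 1 to 4 (Section 6.3): 4 cycles × 3 doses = 12.
- Doses inside the DLT period (Section 7.1): 3 with one intermediate dose (21 days), or 4 with two (28 days).
- Weekly doses after it: 12 − 3 = 9, or 12 − 4 = 8, plus every three-weekly dose from Cycle 5.

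This counts infusions, not risk.

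**The case against.** The strongest reply is that the instructions are not truly opposed. The quoted bullet says when stopping is compulsory; it does not say that non-refractory events may continue. Section 7.2.1 itself sends the site to Table 27, and the usual reading is that a rule specific to the event and the period governs once it is in force. A site that follows Table 27 satisfies both texts, so harm requires someone to act on the general bullet and overlook a cross-reference in the same section. This stands as far as it goes: a careful site would probably stop. It does not remove the gap, because the cross-reference says when Table 27 applies and not that it displaces the override.

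A narrower reading confines the first bullet to the DLT period. Section 4.1 does not settle this. It says that beyond that period "all AEs corresponding to the definition of DLT (see Section 7.1) will be considered for the purpose of determining the RP2D", which concerns dose selection, not re-dosing. Even on the narrower reading, the refractory condition in 7.2.1 still differs from Table 27.

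Section 7.3 is a real safeguard. The protocol describes CRS onset as acute (Section 2.3), so some grade 4 CRS would begin within the 24-hour window and, if judged an infusion-related reaction, would end treatment. CRS starting later, and ICANS outside that definition, remain exposed.

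The dose count says nothing about risk per dose. Routine premedication (first three doses) and the required overnight stays (C1D1 and C1D8) concentrate the CRS precautions in Cycle 1.

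**Conclusion.** The point holds as a conflict of limited scope: escalation only, after the DLT period, for non-refractory grade 4 CRS or ICANS not already stopped by Section 7.3, and for first grade 4 hepatic events that meet DLT criteria. It assumes that the first bullet of 7.2.1 applies to any event meeting the Section 7.1 criteria, whenever it occurs. It merits correction because it bears on re-dosing after a life-threatening event and costs almost nothing to settle.

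A reader might infer more than the documents support:
- *That 7.2.1 simply leaves the decision to the investigator.* Stopping is the default; continuing requires a judgment about both recovery and benefit.
- *That dose finding is compromised.* These grade 4 CRS/ICANS events are DLTs under 7.1 if they occur inside the period, and later events do not enter the mBOIN rates (Section 11.1.7). DLT counts and mBOIN decisions do not change.
- *That the conflict extends to grade 4 pneumonitis through Table 27's other non-hematologic row.* The action cell of that row is cut off in the available text. The SAP dates the pneumonitis risk classification to 29 September 2021, after protocol version 4.0 of 30 March 2021.
- *That subjects were re-dosed.* The documents give no number, grade or timing of such events, so the number affected cannot be estimated.

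The SAP reports that enrollment was stopped and that no expansion data were collected. The practical benefit is therefore to any escalation subject still on treatment and to any reuse of this text.

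**What to change.** Add one sentence to Section 7.2.1: *After the DLT period, the investigator-discretion exception and the 'refractory' qualifier do not apply to events for which Table 27 requires permanent discontinuation, including any grade 4 CRS or ICANS; Table 27 prevails.*

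Leave the rule inside the DLT period, the DLT definition, Table 27 and Section 7.2.2 unchanged. Deleting the word refractory outright would go too far, since it would also alter the rule inside the DLT period, where Table 27 is not in force and no conflict exists. Section 7.2.2 needs no addition because it already refers to Table 27. A general statement that the stricter action governs should be avoided: it would let the stop default in 7.2.1 override Table 27's withhold-and-resume rule for first grade 3 events.

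The cost is one sentence of protocol wording. The small downside is that an investigator could no longer choose to re-dose a recovered subject after such an event.

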# 7.2.2 Expansion Part

- In the event a subject experiences a ≥ grade 2 AE considered drug-related, the GEN1044 dose should be held until the AE resolves to ≤ grade 1. Exceptions are:
  - o Grade 2 CRS
  - Grade 2 ICANS
  - $\circ$   $\geq$  grade 2 fever attributed to CRS
  - $\circ$   $\geq$  grade 2 hypotension attributed to CRS
  - $\circ$   $\geq$  grade 2 hypoxia attributed to CRS,
  - ≥ grade 2 lymphocytopenia

If drug is held for more than 12 weeks, the subject should be permanently discontinued from therapy.

- In cases of cytokine blockade-refractory grade 3 CRS or ICANS lasting >72 hours, GEN1044 must be permanently discontinued.
- In cases of grade 4 CRS or ICANS, GEN1044 must be permanently discontinued.
- In the event a subject experiences a second episode of the same AE at ≥ grade 3, except fever/hypotension/hypoxia attributed to CRS or lymphocytopenia, GEN1044 must be permanently discontinued.
- Refer to Appendix 7, Table 27, for dose modification guidelines for specific adverse events.

# 7.3 Management of Infusion-Related Reactions

Interrupt GEN1044 infusion for IRRs of any severity and institute medical management/supportive treatment as needed.

- For subjects with grade 1, 2, or 3 IRRs, once reaction symptoms resolve, resume the infusion at no more than half the rate at which the IRR occurred. If the subject does not experience any further IRR symptoms, infusion rate escalation may resume at increments and intervals as clinically appropriate.
- For a grade 4 IRR (life-threatening), permanently discontinue administration of GEN1044 and institute appropriate emergency care.

Version: 4.0

# 8 DISCONTINUATION, FOLLOW UP AND COMPLETION

#### 8.1 Discontinuation of Trial Treatment

A subject's trial treatment must be discontinued for any of the following reasons:

- Unacceptable AE requiring treatment discontinuation (see Section 10)\*
- Subject non-compliance
- Sponsor decision
- Pregnancy
- Subject request to discontinue trial treatment\*
- Clinical progression\*
- Radiographic evidence of disease progression
- Other
- \* Imaging should continue to be performed until evidence of radiographic disease progression despite treatment discontinuation. When a subject discontinues trial treatment, he/she is to remain on study and are to be followed until death, initiation of subsequent therapy, or any other reason listed in Section 8.2.

To the greatest extent possible, subjects should be examined as soon as possible, and the treatment discontinuation visit should be performed, irrespective of the reason for discontinuation. If the treatment discontinuation evaluations coincide with a regularly scheduled cycle visit, the treatment discontinuation evaluations will supersede those of the regularly scheduled cycle visit. Subjects should be assessed for adverse events within 30 days of the last administration of trial drug.

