### 4 TRIAL DESIGN

# 4.1 Description of Trial Design

This is a first-in-human (FIH), open-label, multinational, multicenter phase 1/2a trial to evaluate the safety, PK, pharmacodynamics, and preliminary efficacy of GEN1044. GEN1044 will be administered as an IV infusion to a mixed population of subjects with solid tumors. The trial consists of 2 consecutive parts: a Dose Escalation (phase 1) and an Expansion (phase 2a).

In the Dose Escalation part, subjects will be administered GEN1044 according to dose levels outlined in Section 4.2. In the Expansion part, subjects will be administered GEN1044 with the recommended dose(s) from the escalation. GEN1044 will be administered via IV infusion weekly (Q1W) for the first 4 cycles (each cycle is 21 days), followed by every 3 weeks (Q3W), thereafter. Cycle 1 will consist of a priming dose, an intermediate dose, and a full dose. Alternatively, when necessary, Cycle 1 will consist of a priming and 2 intermediate doses, with the first full dose administered on Cycle 2 Day 1. The decision as to whether 1 intermediate dose or 2 intermediate doses will be used for a given cohort will be based on the recommendation of the DEC and confirmed by the Safety Committee (see Section 10.10).

In both parts, subjects will continue to receive GEN1044 until any of the protocol-defined treatment discontinuation criteria are met (refer to Section 8.1). Different doses and schedules might be explored during the Dose Escalation and/or Expansion parts based on the data generated in the dose escalation. Efficacy will be assessed by on-treatment radiological exams/imaging every 6 weeks (±7 days) for 36 weeks, and every 12 weeks (±7 days) thereafter until PD as assessed by the investigator, the start of new anti-cancer therapy, withdrawal of consent, or death, whichever occurs first. For subjects with prostate cancer, efficacy will also be assessed by on-treatment bone scans every 6 weeks (+7 days) (or longer per local standards) for 24 weeks, and every 12 weeks (±7 days) thereafter until PD, the start of new anti-cancer therapy, withdrawal of consent, or death, whichever occurs first. Response assessment criteria relevant to the tumor type (eg, RECIST v1.1 criteria) (Eisenhauer et al., 2009) will be used for response evaluation. Images may be submitted to a central imaging vendor if additional analyses are conducted.

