# 9.2.1.2 Post-Baseline Imaging Assessments

Imaging assessments as described in Table 13 should be performed at the time points specified using the same imaging modality used at baseline, irrespective of trial treatment interruption or actual dosing.

- Imaging assessments (CT/MRI) for response evaluation will be performed every 6 weeks (±7 days) after C1D1 during the first 36 weeks, and every 12 weeks (±7 days) thereafter, or more frequently if clinically indicated.
- For subjects with prostate cancer, bone scans will be performed every 6 weeks (+7 days) (or longer per local standards) during the first 24 weeks, and every 12 weeks (±7 days) thereafter.

Radiological/imaging assessments and bone scans should be scheduled using the first dosing date (C1D1) as the reference date (not the date of the previous tumor assessment) and should be respected regardless of whether treatment with trial treatment is temporarily withheld or unscheduled assessments performed. Radiological/imaging assessments and bone scans should continue until PD, the start of new anti-cancer therapy, the subject withdraws consent, or death, whichever occurs first. (In the case of PD per RECIST v1.1, treatment and imaging assessments may continue in clinically stable (non-prostate cancer) subjects per iRECIST; see below.)

Version: 4.0

Additional imaging assessments may be performed at any time during the trial at the investigator's discretion to support the efficacy evaluations for a subject. Clinical suspicion of disease progression at any time requires a physical examination and imaging assessments to be performed promptly rather than waiting for the next scheduled imaging assessment. Any imaging modalities, if obtained and clinically indicated to assess response or progression, must be entered in the electronic data capture (EDC) pages for evaluation of response or progression.

Each lesion that is measured at baseline must be measured by the same method and when possible, by the same local radiologist/physician throughout the trial so that the comparison is consistent. If an off-schedule imaging assessment is performed because progression is suspected, subsequent imaging assessments should be performed in accordance with the original imaging schedule.

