# 9.2.1.3 iRECIST Assessment of Disease

iRECIST is based on RECIST v1.1 but has been modified to account for the unique response patterns observed with immunotherapy. In this trial, iRECIST will be evaluated as an exploratory endpoint (Seymour et al., 2017).

iRECIST disease progression should be confirmed at least 4 to 7 weeks after the first radiologic evidence of PD in clinically stable participants. Subjects who have disease progression per RECIST v1.1, but unconfirmed disease progression per iRECIST (iUPD), may continue on trial treatment until progression is confirmed as long as the subject is clinically stable. Subjects who are clinically stable must meet the following criteria:

- Subject must have clinical benefit from continuation of trial treatment (as assessed by the investigator) and must not have rapid disease progression
- Subject is tolerating trial treatment
- Subject must have a stable ECOG-PS status
- Treatment beyond progression will not delay an imminent intervention to prevent serious complications for disease progression (eg, CNS metastases requiring immediate treatment).

Any clinically unstable subjects should be discontinued from trial treatment and are not required to have subsequent imaging to confirm PD.

If the subsequent imaging obtained 4 to 7 weeks after the initial assessment of unconfirmed PD confirms disease progression (iCPD), subjects should discontinue trial treatment. If the subsequent imaging shows iRECIST stable disease (iSD), iRECIST partial response (iPR), or iRECIST complete response (iCR), imaging should be continued every 6 weeks ( $\pm 7$  days) and the subject should continue on trial treatment.

Version: 4.0

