# 11.6.18 Exploratory Endpoint – Anti-tumor Activity Based on iRECIST

See Section 11.5.17 where reference is made to iRECIST guideline (Seymour et al., 2017) and the exploratory endpoints iORR, iDCR and iDOR. In addition, the iPFS will be evaluated in the expansion cohorts, and presented similar to PFS, see Section 11.6.8.1. The event date for iPFS is the first date at which progression is met (provided that the progression is confirmed at the next assessment, with exceptions as described in Seymour et al., 2017) or date of death due to any cause, whichever comes first.

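### Section 8.1 requires treatment to stop at radiographic progression while Sections 9.2.1.2 and 9.2.1.3 allow it to continue, so post-progression iRECIST data depend on which section a site follows

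*Protocol*

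**What the plan says.** **Stopping treatment.** Protocol Section 8.1 begins "A subject's trial treatment must be discontinued for any of the following reasons". One item on the list is "Radiographic evidence of disease progression". The item does not say whether progression is by RECIST v1.1 or iRECIST, does not require confirmation, and does not refer to Section 9.2.1.3. Section 4.1 (for both parts), Section 4.8 and Section 6.3 each name Section 8.1 as the place where the stopping criteria are found.

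**Continuing treatment.** Section 9.2.1.2 says that after progression per RECIST v1.1 "treatment and imaging assessments may continue in clinically stable (non-prostate cancer) subjects per iRECIST". Section 9.2.1.3 says that subjects with RECIST v1.1 progression that is still iUPD "may continue on trial treatment until progression is confirmed as long as the subject is clinically stable". It adds conditions on benefit, tolerance and performance status, and says that clinically unstable subjects should come off treatment.

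**Imaging.** The footnote in Section 8.1, which applies to other items on the list, reads "Imaging should continue to be performed until evidence of radiographic disease progression despite treatment discontinuation". Section 9.2 and the imaging rows of Tables 1, 5 and 13 also end scans at progression. Section 9.2.1.3 states that "iRECIST disease progression should be confirmed at least 4 to 7 weeks after the first radiologic evidence of PD in clinically stable participants". If progression is not confirmed, it asks for scans every 6 weeks from then on.

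**Endpoints.** iORR, iDCR and iDOR are exploratory in both parts, and iPFS is added in expansion. Section 11.6.18 dates an iPFS event at first progression, "provided that the progression is confirmed at the next assessment", with exceptions left to the cited iRECIST guideline. Section 11.5.17 excludes prostate cancer from iRECIST.

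**The concern.** The same subject, at the same scan, falls under a mandatory stop in one section and a permission to continue in another. Neither section mentions the other. A site cannot use the permission without breaching Section 8.1 as written.

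The analysis is affected because iRECIST differs from RECIST v1.1 only in what happens after a first progression. If treatment and scanning end there, the data that would separate the two sets of endpoints are not collected. If some sites stop and others continue, the presence of post-progression data depends partly on which section a site reads, and not only on the subject's condition.

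**Working it through.** No sample size, power or event figure is involved, so the check is a comparison of passages plus one calculation on scan timing.

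**1. Who is in conflict.**

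| Subject at first RECIST v1.1 progression | Section 8.1 | Sections 9.2.1.2 and 9.2.1.3 | Conflict |
|---|---|---|---|
| Prostate cancer | stop | permission in 9.2.1.2 limited to non-prostate subjects | no |
| Non-prostate, clinically unstable | stop | stop | no |
| Non-prostate, clinically stable, iUPD | stop | may continue until confirmed | yes |

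**2. What is observed for the third row.**

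- *If 9.2.1.3 is followed:* the subject may stay on drug and is re-scanned. Confirmed progression, or iSD, iPR or iCR on treatment, can be seen.
- *If 8.1 is followed:* the drug stops at that scan. The footnoted imaging duty has already ended, and so have the scans in Section 9.2 and Tables 1, 5 and 13. The treatment discontinuation visit does not fill the gap. Its scan is waived when imaging was done within the preceding 4 weeks (28 days in the table footnotes), which is the likely case when a scan is what triggered the stop. On-treatment response after iUPD is not observed, and confirmation will often be missing.

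**3. Effect on the endpoints where 8.1 is followed.** Responses up to first progression still count, so iORR, iDCR and iDOR can be derived, but they add little to ORR, DCR and DOR. iPFS would often lack the confirming assessment in its definition. How the guideline's exceptions treat such subjects cannot be checked from these documents.

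**4. Scan calendar.** Inputs: scans every 6 weeks to Week 36 and every 12 weeks afterwards, each ±7 days from C1D1 (Section 9.2.1.2); confirmation at 4 to 7 weeks (Section 9.2.1.3, read as a window).

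- Confirmation window: 4 × 7 = 28 to 7 × 7 = 49 days.
- Gap between scheduled scans up to Week 36: 42 ± (7 + 7) = 28 to 56 days. The nominal 42 days is inside the window; a gap of 50 to 56 days is outside.
- Gap after Week 36: 84 ± 14 = 70 to 98 days, which is always outside the window.

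After Week 36 a confirmation scan inside the window must therefore be an extra scan. Tables 1, 5 and 13 do not list one. The instruction in Section 9.2.1.3 to scan every 6 weeks when progression is not confirmed also differs from the 12-weekly schedule that applies by then.

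**The case against.** The best defence is that the exception is written down. Section 9.2.1.2 states the rule that imaging runs until progression and qualifies it at once. The imaging rows of Tables 1 and 5 cite Section 9.2.1, and Table 13 sits within it. A careful reader of the tables can reach the exception. This has force for the tables, but not for Section 8.1, which has no pointer and is where Sections 4.1, 4.8 and 6.3 send the site.

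Several further points stand:

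- The missing footnote mark on radiographic progression in Section 8.1 is not a defect. A duty to image until progression cannot attach to progression itself.
- Sections 9.2.1.2 and 9.2.1.3 give a permission, not an instruction. Some variation between sites at iUPD is built in and would remain after the passages are reconciled.
- A reader might infer from the calendar that progression cannot be confirmed after Week 36. The documents do not support that. Section 9.2.1.2 allows more frequent and additional imaging, so an unscheduled scan can confirm. What remains is that the schedules do not list it.
- A reader might infer that the iRECIST objective cannot be answered at all under Section 8.1 and that its endpoints should be removed. That does not follow. Responses before first progression count, and Section 8.1 does not forbid a confirmatory scan off treatment. The iPFS definition also carries an exceptions clause.

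**Conclusion.** The contradiction is real and stands in the current text. It concerns clinically stable non-prostate subjects with RECIST v1.1 progression that is iUPD. Where Section 8.1 is followed, on-treatment response after iUPD goes unobserved and the confirming scan is often absent. The exploratory iRECIST endpoints then remain computable but say little beyond RECIST v1.1. If sites differ in the section they follow, post-progression data differ with them.

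The number of subjects affected cannot be given. The documents do not report the tumor mix in escalation, so no share of that part can be claimed. Seven of the eight planned expansion cohorts are non-prostate, but SAP Section 2.2 records that no expansion data were collected. Under SAP Section 2.1 efficacy is only listed, and SAP Section 11 covers RECIST v1.1 timepoint response alone, although the SAP's objectives table still carries iORR, iDCR and iDOR. No primary or secondary efficacy endpoint depends on iRECIST. The case for correction rests mainly on two incompatible stopping instructions in one protocol, and less on the loss to an exploratory analysis.

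The conclusion assumes that Section 8.1 is read literally and that sites do not add scans that neither it nor the schedules require.

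**What to change.** 1. Reconcile Section 8.1 with Sections 9.2.1.2 and 9.2.1.3 so that one rule governs RECIST v1.1 progression in clinically stable non-prostate subjects, with a cross-reference between them.
2. Carry that rule into the wording that ends imaging at progression in Section 9.2 and in Tables 1, 5 and 13.
3. If continuation is retained, list the 4-to-7-week confirmation scan in the schedules, including after Week 36, and reconcile the six-weekly interval in Section 9.2.1.3 with the 12-weekly schedule that applies from then.

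Which rule applies is the sponsor's choice. The cost is amendment wording in a few sections and three tables. The confirmation scan is already called for in Section 9.2.1.3, so listing it adds no new procedure.
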